Nutrition. Nutrition-related behaviors will be formally assessed in all participants at T1 and T3. The Three Factor Eating Questionnaire is a 51-item questionnaire developed by Stunkard and Messick (1985) to measure three dimensions of human eating behavior: 1) dietary restraint, or cognitive control of eating behavior, 2) dietary disinhibition, or disinhibition of cognitive control of eating, and 3) susceptibility to hunger. We will only use 18 items of the revised TFEQ from Cappelleri (2009). Participants will complete the consent and survey electronically prior to the Fitbit and Scale delivery.

Theoretical Mediators.

1) A modified version of the Exercise Self-Efficacy scale [47] will be used to assess participants' beliefs in their ability to participate in physical activity. Internal consistencies are good (Cronbach's $\alpha = .99$ across time points). All participants will complete this tool at T1 and T3. 2) Behavioral Skills (e.g. self-regulation) will be assessed using three tools: 1) a 15-item subscale used in Project Grad [48], 2) the Pregnancy Weight Gain and Attitude Scale (PWGAS) ([name], 2003, 2004), and 3) a 3-item scale to assess perceived behavioral control ([name], 2003, 2004). All participants will complete these tools at T1 and T3 3) Social support for physical activity will be measured using two tools: 1) Social Support and Physical activity Scale [49] which assesses perceived social support from both family and friends on a 13-item scale, and 2) the General Social Support Questionnaire (SSW) which measures social support and satisfaction with social support. The SSQ has good test-retest reliability and convergent internal construct validity. All participants will complete these tools at T1 and T3.

Delivery outcomes (i.e., delivery type (vaginal vs. caesarian section), birth weight and gestational age, intervention used (if any), and maternal weight at delivery) will be assessed via self-report survey through REDCap.

Demographics

Socio-demographics (e.g., race/ethnicity, marital status, age, parity, income, education, insurance coverage) will be assessed via baseline survey at T1.

Optional data collection procedures

Participants may be contacted at the conclusion of the study and given the opportunity to choose to participate in a phone or zoom interview to better understand their thoughts about

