participation in the program (to what extent they were satisfied with the program and parts of the program they enjoyed and parts they think could be stronger, etc). The interviews will be approximately 45 minutes long and you will be compensated \$30. Up to 15 women will be invited to participate in an interview. Due to COVID-19, the trial will be run two times; a remote pilot of the trial will be run in the Fall of 2020 (n=30), followed by a larger in-person trial (pending COVID-19) in the Spring of 2021 (n=70)

Interviews with participants will be conducted after the pilot trial (Fall 2020) in addition to after the full trial (Spring 2020).

B. Description of Population to be Enrolled:

We anticipate eligibility screening for pregnant women (6 through 12 weeks) to take approximately 5-10 minutes to complete. The time window for gestational age recruitment was selected based on our formative work [25] [26] that suggests that in order to impact EGWG early intervention is critical. The first 4 weeks of the intervention will consist of educational materials as women may not want to participate in physical activity until near the end of first trimester when their risk for miscarriage drops and the mother tends to feel better physically. The experiential component (i.e., walking and yoga) will start in week 5. In order to extend our recruitment window, we will create rolling recruitment opportunities with women entering into the program from weeks 1 through weeks 6 (weeks 1-4 electronic materials; weeks 5-6 zoom sessions begin). All women will receive the electronic materials for weeks 1-4 before starting the zoom group sessions in week 5. For those women who start the zoom sessions in week 6, they will receive an additional session (material from original week 5) at the end to ensure all women receive 16 sessions (8 weeks of zoom sessions). Women will be recruited from the University of Colorado Clinics, clinics in Denver Metro and surrounding areas as well as social media (e.g. facebook and instagram). We will work with providers to help with recruitment of women in need of intervention for EGWG.

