Inclusion criteria – The population of interest includes English-speaking, pregnant (<13 weeks gestation; or 13-16 weeks gestation and has gained less than 10 lbs in total for women of normal pre-pregnancy weight or less than 5 lbs for overweight/obese) primiparous women, aged 18-46 years, reside in Denver, CO and have medical clearance to exercise during pregnancy. Exclusion criteria include multiparous and having conditions that preclude them from exercising (i.e. HCP has restricted patient from engaging in exercise according to AGOG's absolute contraindications to exercise (e.g. haemodynamically significant heart disease, restrictive lung disease, incompetent cervix/cerclage, persistent second or third trimester bleeding, placenta previa after 26 weeks gestation, premature labor during the current pregnancy, ruptured membranes, and pregnancy induced hypertension).

Protection Against Risk. Every effort will be made to ensure the protection of participants against risk. First, participation is voluntary and participants may refuse to participate or withdraw from the study at any time. Second, participants do not waive any legal rights by consenting to the study. Third, the Principal Investigator and program manager will be

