Throughout the course of this study, we will provide for protection of human subjects. All protocols will be submitted for review and approval to the Colorado Multiple Institution Review Board (COMIRB). All personal data will be kept secure with personal identifiers and study identification numbers maintained in separate, secure, databases. Only the PI and Co-Is will have access. The proposed study is designed to women and overall, the findings of this study may potentially impact the health and wellbeing of women and children.

We have also designed the assessment procedures to minimize burden on participants. Participants will be compensated \$30 per survey completion (T1 and T3; \$60 total/participant). Participants will also receive tickets for a random drawing and chance to receive free diapers for their participation in T2 data collection. Pregnant participants in the MBMM+ intervention group will also receive a yoga mat and pedometer, and both control and intervention groups will receive drawings for free diapers. These types of incentives and amounts are consistent with our other studies at UCH. In addition to the yoga mat and pedometer, the intervention group participants will have the opportunity to keep a Fitbit. If participants attend all sessions 8-16, they will get to keep a Fitbit at the end of the program following post-data collection. If participants in the intervention program attend all but two sessions from sessions 8-16, they will be entered into a raffle for a Fitbit to keep at the end of the program following post-data collection.

F. Data Analysis Plan:

We will use latent growth curve models to separately examine intervention effects on 1) moderate-intensity exercise assessed by the Fitbit and 2) EGWG. These models will then be expanded to examine secondary outcomes (e.g., physical activity, mood, sleep quality, delivery outcomes) and mediators (e.g., exercise self-efficacy, social support, and behavioral skills). For all models, we will control for patient age, ethnicity, parity, risk status, and SES. Primary analyses will be conducted as intent-to-treat, although exploratory as-treated analyses may also be used. Analyses will be conducted primarily using SAS Version 9.2 and Mplus Version 6.0. In closing, the study's proposed approach

is scientifically sound using a tight, randomized controlled trial framework to reduce study bias and increase likelihood of reproducibility.

G. Summarize Knowledge to be Gained:

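### The covariate list spends a place on parity, which eligibility holds constant, and does not name gestational age at T1 or pre-pregnancy BMI for the weight-gain model

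*Combined protocol and SAP*

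**What the plan says.** Section IV.F sets one covariate list for every model: "For all models, we will control for patient age, ethnicity, parity, risk status, and SES". Weight gain and Fitbit-measured exercise are the two lead outcomes, each analysed with a latent growth curve model.

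The inclusion criteria in IV.D describe the population as "primiparous women, aged 18-46 years", and the next sentence begins "Exclusion criteria include multiparous". Parity is also collected as a baseline item: "Socio-demographics (e.g., race/ethnicity, marital status, age, parity, income, education, insurance coverage) will be assessed via baseline survey at T1".

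Two places describe gestational age at entry. Section IV.B expects "eligibility screening for pregnant women (6 through 12 weeks" of gestation. The inclusion criteria accept women under 13 weeks and also women at "13-16 weeks gestation and has gained less than 10 lbs in total" "for women of normal pre-pregnancy weight or less than 5 lbs for overweight/obese".

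The Weight Gain paragraph of IV.A compares total gain with guidelines that depend on pre-pregnancy BMI category and scores it as above, within or below. The randomization text in IV.D mentions a pre-generated table and no stratification factor.

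**The concern.** A covariate helps a randomized comparison when it varies and predicts the outcome. Parity fails the first condition under the plan's own eligibility rules. Two variables that do vary, and that the protocol itself uses in deciding who enters and how weight gain is judged, are not named for the weight model.

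Total gain accumulates with weeks of pregnancy. A woman entering at 6 weeks and one entering at 16 weeks reach T3 at very different gestations, and the gain expected of them also depends on pre-pregnancy BMI. With about 40 completers per arm and no stated stratification, the arms can differ by chance on either variable. The stake is the precision of the weight-gain effect size that Aim 2 is meant to supply to a larger trial.

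**Working it through.** **1. The plan's own figure.** Inputs from Sample Size (IV.B): d = 0.63, alpha 0.05 (sidedness not stated; two-sided reproduces the figure), power 0.80.
- n per arm = 2 × (1.960 + 0.842)² / 0.63² = 39.6, so 40. This agrees with the plan.
- Enrolment at 20% attrition: 40 / 0.80 = 50. This also agrees.
- With the t distribution, 40 per arm gives 79.5% power, which is close enough.

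**2. Parity.** If every woman has the same parity, its column is a multiple of the intercept. A design matrix of intercept, arm and constant parity has three columns and rank two. The coefficient cannot be estimated, no variance is explained and no degree of freedom is used. Removing the term therefore frees none.

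**3. Gestation at T3.** This takes T1 to be at entry and T3 to be 12 weeks later.
- Under IV.B: 6 + 12 = 18 to 12 + 12 = 24 weeks.
- Under the inclusion criteria, with the same lower end: 18 to 16 + 12 = 28 weeks.

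The two windows differ and must be reconciled. Under either one, T3 spans at least six weeks of gestation.

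**4. Chance imbalance.** At 40 per arm, the standard error of the between-arm difference in any one covariate, in SD units, is √(2/40) = 0.224. The 95% range is ±1.96 × 0.224 = ±0.44 SD.

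**5. Cost and gain of two added terms.** This is a linear-model approximation to the growth model for a continuous weight outcome, with N = 80. Two inputs are assumptions, because the documents do not give them:
- The planned terms (age, ethnicity, risk status, SES) plus the T1 value use k₀ = 5, 7 or 9 degrees of freedom. IV.F does not list the T1 value.
- R² is the share of outcome variance that gestational age and BMI explain beyond those terms.

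Expected variance inflation from k covariates is 77/(77 − k). The ratio of the standard error with two added terms to the planned standard error is √[(1 − R²)(77 − k₀)/(75 − k₀)].

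| R² | k₀ = 5 | k₀ = 7 | k₀ = 9 |
|---|---|---|---|
| 0 | 1.014 | 1.015 | 1.015 |
| 0.05 | 0.989 | 0.989 | 0.989 |
| 0.10 | 0.962 | 0.963 | 0.963 |
| 0.20 | 0.907 | 0.907 | 0.908 |

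Example at k₀ = 7 and R² = 0.10: √(0.90 × 70/68) = 0.963.

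Break-even R² = 2/(77 − k₀) = 0.028, 0.029 and 0.029.

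**6. Power.** Noncentral t, k₀ = 7, with d = 0.63 in units of the SD left after the planned terms. The planned model gives 75.5%. With the two terms, power is 74.2%, 76.4%, 78.6% and 83.1% at R² = 0, 0.05, 0.10 and 0.20, a change of about −1, +1, +3 and +8 points.

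**7. Dependence on the form of the outcome.** If every woman gains the same amount per week, total gain by T3 rises with gestational age, but 12-week change equals 12 times the weekly rate whatever the entry week. Entry gestation then explains none of the 12-week change.

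**The case against.** The strongest reply is that a pre-specified list of covariates is a legitimate choice and that the sign of the benefit is unknown: the range above runs from a small loss to a moderate gain. The entry rule limits gain before T1, and only at 13 to 16 weeks, so it does not show that gestation predicts later gain. The illustration is an analysis-of-covariance stand-in for a growth model. It does not apply to the above/within/below score, where BMI category already enters by construction. All of this stands, and it keeps the point small. It does not remove it: the loss is capped at about 1.5%, the variables are already to hand, and the dependence of total gain on weeks pregnant does not rest on the entry rule.

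Several stronger readings are tempting but unsupported:
- **Bias or a wrong sample size.** Randomization protects the comparison on average, and 40 per arm reproduces.
- **Parity costs power.** A constant column costs nothing. 'Primiparous' is not defined, so loose application could leave some variation, but the text gives no sign that this is intended.
- **The models cannot be reproduced because 'risk status' is undefined.** The term has no definition in the text available, but Table 1 and the appendix are cited and not shown. Section IV.B says "We will work with providers to help with recruitment of women in need of intervention for EGWG", so the term might include weight class, but that sentence does not define a covariate. A definition is a useful clarification and no more.
- **A term for trial run is required.** The two runs (n = 30 and n = 70) are in the design, but no stratification by run is stated and run alone probably adds little. It is optional.
- **The same covariates are needed for Fitbit exercise and every other continuous outcome.** Nothing in the documents suggests that they are prognostic there.

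**Conclusion.** The point holds as a low-cost improvement to the weight-gain model only. Parity is constant under the eligibility text as written, and two plausible predictors of total gain by T3 are not named. At 40 per arm, adding both changes the standard error by between about +1.5% (they explain nothing) and −9% (R² of 0.20), with break-even near 0.03. These sizes rest on an assumed R², on 5 to 9 planned degrees of freedom including the T1 value, and on weight gain being analysed as a continuous outcome, which IV.F does not settle. If the outcome is 12-week change, or if 'risk status' already carries BMI, the benefit is smaller and may be nil.

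**What to change.** In IV.F, for weight gain analysed as a continuous outcome, name gestational age at T1 and pre-pregnancy BMI, both continuous, as covariates in place of parity. Keep parity as an eligibility and descriptive item. Say what 'risk status' contains, and if it already includes BMI or weight class, enter that information once. Reconcile the gestational-age windows in IV.B and the inclusion criteria. A trial-run term may be added but is not needed for this point.

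The cost is one or two sentences and no new data collection, since eligibility already requires gestational age and guideline scoring already requires BMI category. The analysis uses up to two more degrees of freedom.
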